### **Protocol Details**

### **Basic Info**

Confirmation Number: **chafhbce**Protocol Number: **820915** 

Created By: [name]

Principal Investigator: [name]

Protocol Title: PFI: BIC Affordable and Mobile Assistive Robots for Elderly Care

Short Title: Affordable Mobile Robots for the Elderly

Protocol Description: This project develops and tests the use of service robots to track health of the elderly over time.

The objectives are to develop a low-cost mobile manipulator capable of a limited set of elderrelevant manipulation tasks (e.g. picking up dropped items). We will visualize and model the use of the service robot during deployments at an elder care facility. Feedback from focus groups with

elders and clinicians will inform the necessary engineering innovation.

Submission Type: **Biomedical Research**Application Type: **EXEMPT Category 4** 

#### Resubmission\*

Yes

### Responsible Org (Department/School/Division):

4482 - RM-Rehabilitation Medicine

### Disclosure of Significant Financial Interests\*

Does any person who is responsible for the design, conduct, or reporting of this research protocol have

#### a FINANCIAL INTEREST?

Nο

### Penn Intellectual Property\*

To the best of the Principal Investigator's knowledge, does this protocol involve the testing, development or evaluation of a drug, device, product, or other type of intellectual property (IP) that is owned by or assigned to the University of Pennsylvania?

Yes

If yes, please provide any readily available information on such IP. For example, a brief description of the IP, any relevant docket number (if disclosed to the Penn Center for Innovation (PCI), patent application or patent numbers, inventor's names, and/or other relevant details.\*

The PI's in are involved in the invention of the system.

#### Certification

I have reviewed the Financial Disclosure and Presumptively Prohibited Conflicts for Faculty Participating in Clinical Trials and the Financial Disclosure Policy for Research and Sponsored Projects with all persons who are responsible for the design, conduct, or reporting of this research; and all required Disclosures have been attached to this application.

Yes

### **Biomedical Research**

### **Human Source Material\***

Does this research include collection or use of human source material (i.e., human blood, blood products, tissues or body fluids)?

No

### **Medical Information Disclosure\***

Does the research proposal involve the use and disclosure of research subject's medical information for research purposes?

Yes

### If the answer is YES, indicate which items is is provided with this submission:

Modified research informed consent document that incorporates HIPAA requirements

### CTRC Resources\*

Does the research involve CTRC resources?

No

### Pathology and Laboratory Medicine Resources\*

Will samples be collected by hospital phlebotomy and/or processed or analyzed by any of the clinical laboratories of the University of Pennsylvania Health System?

No

### Research Involves Apheresis, Cell Collection, and/or Blood Product Collection\*

Does this research involve collection of blood products in the Penn Donor Center and/or the use of apheresis for treatment or collection of cells or other blood components?

No

### Research involving blood transfusion or drug infusions\*

Will your research involve blood transfusion or infusion of study drug in 3 Ravdin Apheresis Unit for research purposes?

No

#### Trial in Radiation Oncology

Is this research a prospective trial being done in Radiation Oncology, and if so, has this protocol been approved by the Radiation Oncology Protocol committee?

N/A

### Study in Radiation Oncology

Is this research a retrospective study being done in Radiation Oncology, and if so, has this project been reviewed by the Radiation Oncology Clinical Research Group?

N/A

### Use of UPHS services\*

Does your study require the use of University of Pennsylvania Health System (UPHS) services, tests or procedures\*, whether considered routine care or strictly for research purposes?

### **Primary Focus\***

Sociobehavioral (i.e. observational or interventional)

### **Protocol Interventions**

x Sociobehavioral (i.e. cognitive or behavioral therapy)

Drug

**Device - therapeutic** 

x Device - diagnostic (assessing a device for sensitivity or specificity in disease diagnosis)

Surgical

x Diagnostic test/procedure (research-related diagnostic test or procedure)

Obtaining human tissue for basic research or biospecimen bank

x Survey instrument

None of the above

### The following documents are currently attached to this item:

There are no documents attached for this item.

Department budget code

None

### **Protocol**

### **Objectives**

### Overall objectives

The goal is to develop in three stages a new affordable robot with the participation of Living Independently for Elders (LIFE) members and clinicians. The robot will be developed by a multidisciplinary team headed by [name] at UPENN (PI), [name] at Savioke, and Drs. [name] and [name] at UPENN PM&R and UPENN Nursing respectively. We aim to build a low-cost robot platform that will focus on the simple, but key, repetitive, data-driven tasks that robots do well. Rather than attempt to create a robot helper that mimics humans, we aim to free human caregivers from the time-consuming tasks that robots can accomplish with facility, thereby allowing humans to focus on tasks that humans do best (i.e. human contact). Participatory reviews of the developed prototypes will be completed at each stage (each year) with the LIFE members and clinicians. There are three research questions we hope to answer all while building an effective system to synergistically satisfy the business needs: R1) Although activities of daily living (ADLs) for elder health have previously been documented and categorized, no research has been done to characterize them from the perspective of their feasibility of automation using an affordable mobile manipulation robot. How can we characterize known ADLs according to how much they would benefit from robotic assistance given varying levels of

robot capabilities (mobility, limited manipulation, full manipulation)? R2) A manipulator arm must be safe, affordable, and performant enough to assist in ADLs for elder heath. What new breakthroughs are required to develop new manipulation technology that satisfies these constraints? What are the concomitant key usability and acceptance of service features required? R3) A data-driven service robotics system has the potential to affect elder health in a positive way. How can predictive service robotics best be used to maintain and improve elder health? Which specific robot behaviors have the most impact on elders' well-being?

### **Background**

A growing elderly population coupled with low birth rates in the developed world is creating a crisis in healthcare. The number of senior citizens is outgrowing the number of working-age adults to care for them. In the US alone, the number of seniors over age 65 is projected to double from year 2000 to 2030, reaching 71.5 million. Similar statistics are found throughout the world. With the scarcity of care options available, robots are a welcome solution for assisting elders with small tasks that would normally be done by a caregiver. With an estimated 17,000 elder care facilities nationwide, merely placing a single affordable robot in each facility would result in a \$170m business. In this vein, the past decades have seen an enormous amount of robotics research funded by institutions such as the NSF and DARPA, including a notable multi-million dollar effort by the European Union in the RoboEarth project which aims at hospital service. A variety of companies have also explored robots in the healthcare space. Aethon, Vecna, and Helpmate have automated materials transport/delivery with varying success. They have limited service capability in that they are not capable of manipulation. On the other side of capability, research robots such as Willow Garage's PR2 and Care-o-bot from Fraunhofer IPA have demonstrated mobile manipulation, but have costs between \$100-500K. Fortunately, a number of factors are converging to make cost-effective robots possible now. Previous efforts have exploited rapid prototyping low-cost hardware such as 3D printing and mass customization of electronics to lower hardware costs. Additionally, the software necessary to power mobile manipulation robots and hardware costs, such as low-cost depth sensors (i.e. Microsoft's Kinect) are becoming better and cheaper each year. Through our own novel design and innovation coupled with capitalizing on the various factors that are precipitously driving down the costs of necessary components, we aim to develop an affordable and capable robot that will address the demographic shift towards the need for more elderly care. One key to making this system viable is maintaining effectiveness at low cost. This work will build on existing navigation and control software for mobile robots using a platform being commercialized by Savioke. On top of this, a new low-cost expanding prismatic joint arm developed at University of Pennsylvania will add manipulation capabilities. This hardware and software platform will enable the study of the usefulness of robots in an elder care facility. Limited tasks such as the delivery of water to patients can be used to monitor hydration of individuals over-time and pro-actively predict required service to aid in healthcare. The information gathered by these robots and how elders use them during field use will help to learn how robots can help create a larger data-driven health monitoring system. The partners include the University of Pennsylvania's School of Engineering and Applied Science, School of Medicine, School of Nursing (Philadelphia PA), and Savioke (Sunnyvale, CA, a small business concern) along with LIFE, Living Independently For Elders (Philadelphia PA).

### Study Design

### Design

We plan to tackle the myriad aforementioned challenges in three stages. First, based on focus group feedback, we will design a data collection plan for the robot to collect information about service tasks. This may include information such as the time it takes the robot to perform a task, when the task was requested, whether the robot succeeded at performing the task, etc. This data collection component will be deployed at LIFE or a LIFE-affiliated retirement community during the various trials. Additionally, our partners at Savioke ([name] is a co-PI on the NSF grant) will conduct additional focus groups in elderly care facilities in California, in order to get faster feedback on their prototype designs. The focus group methodology will be employed throughout to assess user needs and evaluate user experiences with the robot system being developed. Second, we will develop interactive data visualizations of the collected data and share these with the LIFE and LIFE-affiliated administrators, staff, and residents. These interactive data visualizations will make use of best practices in medical informatics and visualization and enable stakeholders to explore the data we have collected and from initial conclusions about resident's health and service needs. Based on feedback from the visualizations, we will fine-tune our data collection process which will likely impact the robot design. The final step will be to develop

predictive models of when people want services performed so that our system can proactively deliver services when they are needed. By tracking residents' requests over time - a machine learning problem - we aim to build a model of what features in the environment trigger the service requests over time.

### **Study duration**

1) We estimate that it will take three years from the date of IRB approval to enroll all subjects and complete the study. 2) A subject may choose to participate for as little as one focus group (1.5 - 2 hours) or may choose to participate in each part of the larger study over the course of three years. 3) 8/15/2014 - 8/15/2017

### **Characteristics of the Study Population**

### **Target population**

1. Three populations will be involved: 1. Elders who are members of Living Independently For Elders (LIFE) run by the University of Pennsylvania, School of Nursing and their caregivers will be recruited for the study. The elder members will be drawn from those participating in the LIFE-affiliated retirement community (Mercy Douglas or Kearsley) or those on the Council of Elders for LIFE or those at LIFE. Elders must be members of LIFE and live at a LIFE-affiliated retirement community or participate in the elder council. Members of LIFE are age 55 and older, in need of medical care or supportive services, are state-certified as nursing home eligible, live in certain areas in Philadelphia County, Pennsylvania, prefer to continue living in their community for as long as possible, can be safely served and able to pay privately or through Medicare. Members of LIFE at Kearsley and Mercy Douglas require more assistance with physical, cognitive and social functioning and are provided a 24hour interdisciplinary clinical staff to assist them in meeting needs. Members are 62 years and older, in imminent risk of a nursing home placement, attends LIFE center daily (day program), able to have activities of daily living (ADL) needs met by caregivers, able to pay required rent for apartment, and able to function safely in community with other elders. And for the purpose of earlier prototyping and obtaining faster feedback on designs, Savioke may conduct additional focus groups at The Forum at Rancho San Antonio a Continuing Care Retirement Community located in Silicon Valley. 2. Clinicians: Clinicians will be recruited from the clinical staff working at LIFE, Kearsley, and Mercy Douglas which consists of primary care physicians, nurses and nurse practitioners, certified nursing assistants, home health aides, licensed social workers, physical and occupational therapists, personal care workers, etc. Subjects will also be excluded if they do not understand the study and refuse to comply with procedures. Subjects will be excluded if they are unable to cognitively give consent. For the corn toss game, 30 participants will be recruited who are able to use both arms and reach up towards a cabinet, have a minimental score of 20 or higher, and are able to stand and reach

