### **Subject recruitment**

[name] (UPENN Nursing Professor) and [name] (Interim Chief Nursing Officer) are affiliated with LIFE and will be responsible for reviewing LIFE's medical records. After potential study participants are identified, the commonly used Short Blessed Test (measures cognitive function in the elderly), SF-12, etc., may be administered for additional screening purposes. LIFE members will then be consented prior to participation in the focus groups by a member of the research team. For any focus groups at The Forum at Rancho San Antonio, Savioke will liase with the Director of Wellness, [name], with whom they have an established relationship. Residents at The Forum will then be consented using the same consent form used for any LIFE members. Recruitment will be word of mouth, direct solicitation, and informational sessions convened with the assistance of the Council of Elders' and the research committee overseeing participant activities.

Will the recruitment plan propose to use any Penn media services (communications, marketing, etc.) for outreach via social media avenues (examples include: Facebook, Twitter, blogging, texting, etc.) or does the study team plan to directly use social media to recruit for the research?

No

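### Does naming LIFE attendees as a source of elders contradict the rule that elders must live at an affiliated community or sit on the elder council?

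*Protocol*

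**What the plan says.** All the wording at issue is in the protocol. The Target population section names the affiliated communities (Mercy Douglas and Kearsley) as a source of elders and continues "or those on the Council of Elders for LIFE or those at LIFE". It then states the requirement: "Elders must be members of LIFE and live at a LIFE-affiliated retirement community or participate in the elder council".

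The same section describes two groups. For the general membership it says "Members of LIFE are age 55 and older". For the two communities it says "Members of LIFE at Kearsley and Mercy Douglas require more assistance with physical, cognitive and social functioning", followed by "Members are 62 years and older, in imminent risk of a nursing home placement". It adds that this second group goes to the LIFE centre every day.

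The corn toss has criteria of its own: "For the corn toss game, 30 participants will be recruited who are able to use both arms and reach up towards a cabinet", together with a mini-mental score of at least 20 and the ability to stand and reach. Neither residence nor council membership is mentioned there.

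Under Subject recruitment, two nursing staff affiliated with LIFE "will be responsible for reviewing LIFE's medical records", and after candidates have been identified, "LIFE members will then be consented prior to participation in the focus groups by a member of the research team".

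**The concern.** Two adjacent sentences appear to define different populations. Someone who attends LIFE, lives elsewhere and is not on the council is named as a source and then shut out by a mandatory condition. Staff working from the first sentence could enrol such a person, and a monitor working from the second could record an eligibility deviation.

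The choice would also affect the make-up of the sample. Membership starts at 55 and the residents' description starts at 62. Under the stricter sentence, members aged 55 to 61 could enter only through the council, and every elder not on the council would come from the group described as needing more help. Who may enrol is a protocol matter, so this cannot be left to a statistical analysis plan.

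**Working it through.** The protocol gives no figure to reproduce. The check is one of logic, followed by a reading of each activity.

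**Logic.** Let M mean LIFE member, R resident of an affiliated community, C on the elder council, and L at LIFE.

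- Source sentence: R or C or L.
- Requirement, first grouping: M and (R or C).
- Requirement, second grouping: (M and R) or C.

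Take an elder with M = 1, R = 0, C = 0, L = 1:

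- Source sentence: 0 or 0 or 1 = true.
- First grouping: 1 and (0 or 0) = false.
- Second grouping: (1 and 0) or 0 = false.

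The grouping of the and/or therefore does not remove the mismatch. One combination of attributes is affected. This counts a type of member, not people.

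**Age.** The difference between the two floors is 62 − 55 = 7 single years of age (55 to 61). This follows from applying the stricter sentence and is not a second inconsistency.

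**Where the boundary could matter, activity by activity (Procedures section).**

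- *Year 1 needs-assessment groups:* the LIFE elders are council members, so they meet the requirement.
- *Year 2 walking and hydration tasks:* these take place at or in the participant's apartment, which fits residents, so the requirement is met.
- *Corn toss:* it may be run at Mercy Douglas or at LIFE, and its added criteria concern function and cognition. The boundary could matter here.
- *Year 3 testing:* it may be run at LIFE, at an affiliated community, or at both. The boundary could matter here too.

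**What would follow in the two open activities.** In the corn toss the same participants play under each retrieval condition: fetching the bags themselves, having a team member fetch them, and two robot conditions. A wider or narrower pool changes whom the comparison describes. It does not unbalance the conditions, because each person contributes to all of them. For Year 3 the stated output is usability feedback to the development team. The Analysis Plan section describes content coding of transcripts, demographic summaries and usability measures such as ease of use, set-up time, faults and hours without error. It states no hypothesis test or threshold that the eligibility boundary could shift.

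**The case for a change.** The strongest case for acting is that the wording cannot be fully harmonised. If those at LIFE were only residents and council members, the third source would add nobody. The section also describes the general membership separately from the Kearsley and Mercy Douglas residents, and LIFE is named as a site distinct from the communities in both the Design and Procedures sections. Subject recruitment speaks of LIFE members without repeating the residence-or-council condition. An amendment would take only a sentence or two.

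Part of this stands: the requirement does omit a source that has just been named, and the text does not say why. The rest is weaker.

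- A source may be wider than the eligibility rule applied to it. Reviewing all of LIFE's records and then applying a condition is ordinary screening.
- The phrase for the third source is undefined. Affiliated residents attend the LIFE centre daily, so it can describe a place where eligible elders are found.
- A test site says where the robot operates, not who qualifies.
- Consent under Subject recruitment comes after candidates have been identified, so the condition may already have been applied. Not repeating it there does not create a second rule.
- The corn toss criteria can be read as additions to the general rule.

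A low cost does not by itself justify an amendment. The suggested repair leaves open which sentence should give way, and neither choice is shown to improve precision, bias, safety or the ability to answer the research questions.

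**Conclusion.** The mismatch is genuine but is a looseness of drafting, and no change to the plan is needed. With the mandatory sentence taken as controlling, the plan can be carried out as written. The council groups and the apartment-based tasks already satisfy that sentence, and the remaining doubt is confined to the corn toss (30 participants) and Year 3 testing.

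No effect on power or on any stated result is shown. The number of elders concerned cannot be derived, because the protocol does not count members who are neither residents nor on the council.

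This conclusion rests on two assumptions: that staff treat the word must as the operative condition, and that the general elder rule carries over to activities with added criteria. If the team instead admitted other LIFE members to those two activities, the group described would be more mixed in age and function. The demographic summaries already planned would show the age mix.

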### Subjects enrolled by Penn Researchers

155

### Subjects enrolled by Collaborating Researchers

0

### Vulnerable Populations

**Children Form** 

Pregnant women (if the study procedures may affect the condition of the pregnant woman or fetus) Form

Fetuses and/or Neonates Form

**Prisoners Form** 

Other

x None of the above populations are included in the research study

### The following documents are currently attached to this item:

There are no documents attached for this item.

### **Subject recruitment**

[name] (UPENN Nursing Professor) and [name] (Interim Chief Nursing Officer) are affiliated with LIFE and will be responsible for reviewing LIFE's medical records. After potential study participants are identified, the commonly used Short Blessed Test (measures cognitive function in the elderly), SF-12, etc., may be administered for additional screening purposes. LIFE members will then be consented prior to participation in the focus groups by a member of the research team. For any focus groups at The Forum at Rancho San Antonio, Savioke will liase with the Director of Wellness, [name], with whom they have an established relationship. Residents at The Forum will then be consented using the same consent form used for any LIFE members. Recruitment will be word of mouth, direct solicitation, and informational sessions convened with the assistance of the Council of Elders' and the research committee overseeing participant activities.

Will the recruitment plan propose to use any Penn media services (communications, marketing, etc.) for outreach via social media avenues (examples include: Facebook, Twitter, blogging, texting, etc.) or does the study team plan to directly use social media to recruit for the research?

No

